4.2.2. Main analytical approach

4.2.2.1. Adverse events and serious adverse events

An adverse event (AE) is considered study intervention emergent if the AE onset date is on or after study intervention start date. All AE summaries will be based on study intervention emergent events unless otherwise specified. SAE summaries will be based on all SAEs reported regardless of whether they meet the definition of study intervention emergent or not.

Adverse event analysis will be based on GSK Core Data Standards.

The proportion of participants reporting AEs will be tabulated by study intervention and by dose.

The following displays for Adverse events ((All AEs, Grade 2 or higher, and SAEs)) will be generated: Overview of Adverse Events, Summary of All Adverse Events, Summary of Taste Adverse Events, Summary of Drug-Related Adverse Events, Summary of Adverse Events Leading to Permanent Discontinuation of Study Treatment, Summary of Adverse Events Leading to Withdrawal from Study. These displays will be tabulated by System Organ Class and Preferred Term.

Further details of the planned displays will be given in OPS.

4.2.2.2. Laboratory Data, Vital Signs, ECGs

For haematology, clinical chemistry, urinalysis, vital signs, ECG and spirometry data the following information will be summarised:

- 1) Clinically significant values at each visit
- 2) Raw and change from baseline values at each visit

Note: The first table is the only one included as part of the primary endpoint. Urinalysis data is only collected when there is an abnormal finding and so it is expected that urinalysis tables/listings will be sparse.

Laboratory Data

For laboratory data, separate tables for haematology, clinical chemistry and urinalysis tests will be produced. Laboratory evaluations including the analyses of Clinical chemistry tests, haematology tests and urinalysis, will be based on GSK Core Data Standards. Liver biochemical parameters will be included with clinical chemistry tests.

The details of the planned displays will be given in the OPS. Incidence of clinically significant laboratory parameters will be reported.

Vital Signs

The analyses of vital signs will be based on GSK Core Data Standards, unless otherwise specified.

In vital sign assessment, pulse rate, respiratory rate, tympanic temperature, and systolic and diastolic blood pressure will be assessed. Blood pressure and pulse measurement will be taken in the semi supine position.

Incidence of clinically significant vital sign parameters will be reported. Refer the normal ranges of laboratory parameters in the Section [6.2.1](#)

Further details of the planned displays will be given in OPS.

ECG

The QTc data analysis will use the collected values based on Fridericia formula.

The analysis of 12-lead ECG along with any ECG findings will be reported according to GSK Core Data Standards.

Safety ECGs will be performed in semi-supine position after at least 5 minutes rest. The parameters collected are PR, QRS, QT and QTc intervals.

Incidence of clinically significant ECG parameters will be reported. Refer the normal ranges of laboratory parameters in the Section [6.2.1](#)

Further details of the planned displays will be given in OPS.

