8.2.5. Clinical Safety Laboratory Tests

- See [Appendix 2](#) for the list of clinical laboratory tests to be performed and the SoA for the timing and frequency.
- The investigator must review the laboratory report, document this review, and record any clinically significant changes occurring during the study as an AE. The laboratory reports must be filed with the source documents.
- Abnormal laboratory findings associated with the underlying disease are not considered clinically significant, unless judged by the investigator to be more severe than expected for the participant's condition.
- All laboratory tests with values considered clinically significantly abnormal during participation in the study should be repeated until the values return to normal or baseline or are no longer considered significantly abnormal by the investigator or medical monitor.
 - If clinically significant values do not return to normal/baseline within a period of time judged reasonable by the investigator, the etiology should be identified and the sponsor notified.
- All protocol-required laboratory tests, as defined in [Section 10.2](#), must be conducted in accordance with the laboratory manual and the SoA ([Section 1.3](#)).
- If laboratory values from non-protocol specified laboratory tests performed at the institution's local laboratory require a change in participant management or are considered clinically significant by the investigator (e.g., SAE or AE or dose modification), then the results must be recorded.

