9.4.2.2. Laboratory values, vital signs, 12-lead electrocardiogram and Spirometry

Whilst all data collected will be summarized, only measurements which are clinically significant at any timepoint between randomization and follow up will be reported as part of the primary endpoint. Potential clinical interest (PCI) ranges will be defined in the SAP.

This data includes:

- Laboratory results for hematology, clinical chemistry and urinalysis (see [Appendix 2](#) for full details).
- Vital Signs measurements for semi supine systolic and diastolic blood pressure, pulse rate, respiratory rate and temperature.
- 12-lead safety electrocardiogram (ECG) measurements for heart rate, PR, QRS, QT and QT interval corrected for heart rate according to Frederica's formula (QTcF) intervals.
- Spirometry measurements for FEV1.

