4.2.1. Definition of endpoints

Adverse events will be coded using the latest standard Medical Dictionary for Regulatory Affairs (MedDRA dictionary).

Grade 1 AEs are defined as mild. Grade 2 or higher AEs are defined as moderate or severe. This study will report AEs as mild, moderate, or severe.

CONFIDENTIAL

A study intervention-related AE/SAE is defined as an AE/SAE for which the investigator classifies the possible relationship to study intervention as “Yes”. A worst-case scenario approach will be taken to handle missing relatedness data, i.e., the summary table will include events with the relationship to study intervention as ‘Yes’ or missing.

Spirometry assessments are performed in triplicate with the highest value reported.

Whilst all data collected will be summarized, only measurements which are clinically significant at any timepoint between randomization and follow up will be reported as part of the primary endpoint.

Clinically significant values are defined as:

- Values in the potential clinical interest (PCI) ranges for laboratory values, vital signs, ECGs and spirometry.
- Values that achieve the study stopping criteria (protocol Section 7.1.3) for spirometry

The PCI ranges will be defined in the Section [6.2.1](#).

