6.2. Appendix 2 Data Derivations Rule

6.2.1. Criteria for Potential Clinical Importance

- **Laboratory Values**

Haematology				
Laboratory Parameter	Units	Category	Clinical Concern Range	
			Low Flag (<x)	High Flag (>x)
Platelet Count	10 ⁹ /L		31	900
RBC Count	10 ¹² /L		4.2	5.9
Hemoglobin	g/L	Male	90	180
		Female	90	180
Hematocrit	fraction of 1			1.5*ULN
RBC Indices				
MCV	fL		0.75*LLN	1.5*ULN
MCH	pg		28	32
%Reticulocytes	%		na	2*ULN
WBC Count with differentials				
Lymphocytes	10 ⁹ /L		0.6	6
Neutrophil Count	10 ⁹ /L		1.5	12
Monocytes	10 ⁹ /L		na	2
Eosinophils	10 ⁹ /L		na	0.5
Basophils	10 ⁹ /L		na	2*ULN

CONFIDENTIAL

Clinical Chemistry				
Laboratory Parameter	Units	Category	Clinical Concern Range	
			Low Flag (<x)	High Flag (>x)
Albumin	g/L		32	50
Calcium	mmol/L		2.2	3.24
Creatinine	umol/L	Male 40-49 years	69	106
		Male 50-59 years	67.2	106
		Male 60-69 years	67.2	106
		Male 70+ years	59.2	106
		Female 40-49 years	52.2	106
		Female 50-59 years	53	106
		Female 60-69 years	53	106
		Female 70+ years	55.7	106
Glucose	mmol/L		4.0	7.8
BUN	mmol/L		2.5	15
Potassium	mmol/L		3.5	5.2
Sodium	mmol/L		136	145

CONFIDENTIAL

Liver Function			
Test Analyte	Units	Category	Clinical Concern Range
Alanine Aminotransferase (ALT) / Serum Glutamic-Pyruvic Transaminase (SGPT)	U/L	High	≥2x ULN
Aspartate Aminotransferase (AST) / Serum Glutamic-Oxaloacetic Transaminase (SGOT)	U/L	High	≥2x ULN
Alkaline phosphatase	U/L	High	≥2x ULN
T Bilirubin	μmol/L	High	≥ 1.5x ULN
Direct Bilirubin	μmol/L		0 – 6

- **ECG**

ECG Parameters	Unit	Clinical Concern range	
		Lower(<x)	Upper(>x)
Absolute			
Absolute QTc Interval	msec		> 600
Absolute PR Interval	msec	< 85	> 240
Absolute QRS Interval	msec	< 70	> 120
Change from Baseline			
Increase from Baseline QTc	msec		> 60

- **Vital Signs**

Vital Parameters (Absolute)	Unit	Clinical Concern range	
		Lower(<x)	Upper(>x)
Heart rate	bpm	35	110
Respiratory Rate	breaths/pm	8	20
Systolic blood pressure	mmHg	95	160
Diastolic Blood Pressure	mmHg	55	100
Temperature	°C	35.6	37.7

- **Spirometry**

Any participant experiencing a reduction in FEV1 at the 1-hour post-dose compared to daily pre-dose value of > 20%.

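### The urinalysis table of clinically significant values in the primary endpoint is empty by construction, because SAP 6.2.1 has no urinalysis criterion; total WBC and total protein are lesser gaps

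*SAP*

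**What the plan says.** Protocol 9.4.2.2 lists the data that feed the laboratory part of the primary endpoint, beginning with "Laboratory results for hematology, clinical chemistry and urinalysis", and leaves the PCI ranges to the SAP.

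SAP 4.2.1 restricts what counts: "only measurements which are clinically significant at any timepoint between randomization and follow up will be reported as part of the primary endpoint". For laboratory data it gives one definition of clinically significant: "Values in the potential clinical interest (PCI) ranges for laboratory values, vital signs, ECGs and spirometry". The only other definition there concerns spirometry. On location it says "The PCI ranges will be defined in the Section" 6.2.1.

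SAP 4.2.2.2 plans two displays per visit: "For haematology, clinical chemistry, urinalysis, vital signs, ECG and spirometry data the following information will be summarised", namely clinically significant values, then raw and change-from-baseline values. It assigns only the first to the primary endpoint. On urinalysis it adds "Urinalysis data is only collected when there is an abnormal finding" and expects sparse output as a result.

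SAP 6.2.1 covers haematology, clinical chemistry, liver function, ECG, vital signs and spirometry. It has no urinalysis entry. "WBC Count with differentials" appears as a group heading without a limit, and total protein has no row.

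Protocol 8.2.5 separately requires the investigator to "record any clinically significant changes occurring during the study as an AE".

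**The concern.** A table whose inclusion rule no value can satisfy carries no information. If the SAP is followed as written, the urinalysis table in the primary endpoint shows zero clinically significant values in every arm and at every visit. A reader of the study report could take that as a safety finding when no criterion existed.

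The second urinalysis table, raw and change from baseline, has a different problem. If normal results are not recorded, the transition of most interest, normal before dosing and abnormal after, cannot appear as a change. The number tested would also be unknown, because a normal result and a test not done would look the same.

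**Working it through.** **The plan's own figures.** The only design figures are the chances of seeing at least one event, 1 − (1 − p)^n (SAP Section 5).

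| n on active | true rate p | 1 − (1 − p)^n | stated |
|---|---|---|---|
| 9 | 5% | 1 − 0.6302 = 37.0% | 37% |
| 9 | 20% | 1 − 0.1342 = 86.6% | 87% |
| 6 | 5% | 1 − 0.7351 = 26.5% | 27% |
| 6 | 20% | 1 − 0.2621 = 73.8% | 74% |

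They reproduce to within a percentage point. The point here does not depend on them, but they give a contrast: for a urinalysis value to enter the PCI table the chance is 0 at any p and any n.

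**Matching protocol Table 4 to SAP 6.2.1.**

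| Group | Required in Table 4 | With an entry in 6.2.1 | Without |
|---|---|---|---|
| Haematology | 13 | 12 | total WBC |
| Chemistry including liver | 13 | 12 | total protein |
| Urinalysis (dipstick) | 10 | 0 | all 10 |
| Total | 36 | 24 | 12 |

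The 10 urinalysis parameters are specific gravity, pH, glucose, protein, blood, ketones, bilirubin, urobilinogen, nitrite and leukocytes.

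**Does the omission look intended?** The documents do not say so. SAP 4.8, which lists departures from the protocol's analysis, names only FVC. The version history records that 6.2.1 was revised because its ranges and units did not match the laboratory's values, and the gaps remain. The WBC heading is laid out like the RBC indices heading, so a limit lost in text extraction is unlikely.

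**The collection sentence against the schedule.** The protocol's schedules list urinalysis at screening, on Day -1 of each period, and twice more in Period 3 (apparently Days 6 and 13). A participant who completes the study has 1 + 3 + 2 = 6 scheduled tests, with one more visit for early discontinuation. Table 4 then allows optional further urine tests after certain positive dipstick results and says those results are kept in the database. The SAP sentence may mean only these reflex tests, but it is worded for urinalysis data in general.

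**Consequence on the literal reading.** SAP 4.1.2 derives nothing when baseline is missing.

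| Baseline | Later visit | What is recorded | Change from baseline |
|---|---|---|---|
| normal | normal | neither | none |
| normal | abnormal | later only | none |
| abnormal | normal | baseline only | none |
| abnormal | abnormal | both | available |

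Only one of the four patterns gives a change, and it is not the one of interest. If the sentence covers only reflex tests, this consequence falls away; the missing PCI criterion does not.

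**The case against.** The strongest objection concerns consequence. A reader might infer that the primary endpoint can report no clinically significant urinalysis, total WBC or total protein change at all. The documents do not support that. The endpoint's first component is adverse events. Protocol 8.2.5 makes significant laboratory changes reportable as such, and Appendix 3 (10.3.1) names haematology, chemistry and urinalysis. Except for findings tied to the underlying disease and no worse than expected, a change the investigator judges significant therefore enters the endpoint. This stands: the defect lies in the laboratory table.

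Total WBC and total protein are also partly covered. All five differentials and albumin have limits, and both analytes still receive raw and change summaries. This largely stands, though the cover is loose: with neutrophils at 12, lymphocytes at 6, monocytes at 2 and eosinophils at 0.5, total WBC is 12 + 6 + 2 + 0.5 = 20.5 × 10⁹/L before basophils with none of those four flagged. Albumin is only one part of total protein.

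A reader might also infer that change from baseline certainly exists only for participants abnormal at both times, or that means will be taken over abnormal results. The first rests on the literal reading of an ambiguous sentence. The second is not stated: SAP 4.1.1 summarises categorical data as counts and percentages, and the display specification (OPS) and sponsor data standards are not available here. They do not supply the missing criterion, however, since SAP 4.2.1 assigns the ranges to 6.2.1.

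Finally, this is a descriptive study of about 12 participants without hypothesis tests, and its stopping criteria do not use these flags. That limits the weight of the point but does not make an empty table informative.

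**Conclusion.** The point holds for the planned laboratory displays. Under the SAP's own definition, none of the 10 urinalysis parameters can be flagged, so the urinalysis table in the primary endpoint is empty by construction. Total WBC and total protein add two smaller gaps, making 12 of 36 required parameters without an entry. The practical risk is misreading an empty table as evidence of no significant change; the adverse event component can still capture what the investigator judges significant.

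The missing criterion follows from the text and needs no assumption about event rates. The missing-change argument is conditional on normal dipstick results not being recorded, and the documents leave that open. In either case the SAP sentence and the protocol need reconciling.

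**What to change.** 1. Reconcile the collection sentence in SAP 4.2.2.2 with the protocol's schedule and Table 4. Treat every scheduled dipstick result as data, including normal ones. Protocol 8.2.5 requires laboratory reports to be filed with the source documents, so normal results should be recoverable without new tests.
2. Replace the urinalysis PCI and change-from-baseline tables with one categorical display: abnormal results as n over number tested at each scheduled visit, split by new versus already present at the SAP 4.1.2 baseline, the last value before first dose. Name that baseline explicitly, because each of the three periods has its own Day -1.
3. Add PCI limits for total WBC and total protein, or state that they are excluded from the PCI table and that significance is captured through adverse events.

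The cost is minor SAP wording and some data entry, with back-filling for completed visits if normal results were not entered. A dipstick-abnormal category is less specific than a numeric limit. It also gives more than a second count of investigator-judged events, which the adverse event tables already contain.

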4.2.2.3. Lung Function Measurements

Spirometry

Spirometry data will include FEV1 measurements.

For spirometry data the following information will be summarised:

- 1) Clinically significant values at each visit
- 2) Raw and change from baseline values at each visit

4.3. Secondary Endpoint(s) Analyses

All pharmacokinetic analyses will be performed on the PK Population.

For PK endpoints, all analysis will be performed by Part i.e., Part A (Periods 1 and 2, single dose) and Part B (Period 3, repeat dose), except dose proportionality, which will be carried out using data from the three periods.

From the plasma concentration-time data, the following pharmacokinetic parameters will be determined if data permitting, for each dose of GSK3923868:

- Treatment period 1 & 2 (single ascending doses): AUC(0-t), AUC(0-24), AUC(0-6), Cmax and Tmax
- Treatment period 3 (repeat dose): Cmax, Tmax and AUC(0-6) on Day 1 and Day 14

4.3.1. Key secondary endpoint(s)

4.3.1.1. Definition of endpoints

Parameter	Parameter Description
AUC(0-t)	Area under the concentration-time curve from time zero to the time of the last quantifiable concentration (C(t)) will be calculated using the linear trapezoidal rule for each incremental trapezoid and the log trapezoidal rule for each decremental trapezoid.
AUC (0-24)	Area under the concentration-time curve over the dosing interval.
Cmax	Maximum observed concentration, determined directly from the concentration-time data over the dosing interval.
Tmax	Time to reach Cmax, determined directly from the concentration-time data over the dosing interval/
AUC (0-6)	Area under the concentration-time curve from time 0 to 6-hour post dose.

NOTE: Additional parameters may be included as required.

4.3.1.2. Main analytical approach

Plasma GSK3923868 concentration-time data will be analyzed by non-compartmental methods with WinNonlin. Calculations will be based on the actual sampling times recorded during the study.

Pharmacokinetic data will be presented in graphical and/or tabular form and will be summarised descriptively.

4.3.1.3. Dose Proportionality

The following pharmacokinetic statistical analyses will only be performed if sufficient data are available (i.e., if more than 5 subjects have well defined plasma profiles). If the dose with limited data is at the lower end of the dose range, the data will be excluded, and the appropriate analysis conducted on the rest of the data. However, if there are non-calculable PK parameter data at intermittent doses no statistical analyses will be performed. The assessment of dose proportionality will utilise Period 1,2 and the first dose of Period 3 data only.

Dose proportionality will be assessed using power method as primary, and ANOVA as supportive method:

Pharmacokinetic Statistical Analyses for Dose Proportionality: Power Method
Endpoint(s)

 AUC(0-6), Cmax Each endpoint to be assessed separately.
Model Specification

 $\log_e(Y) = \beta \times \log_e(\text{dose}) + \log_e(\alpha)$ where Y is the pharmacokinetic parameter and $\log_e(\alpha)$ is an intercept term.
Model Results Presentation

 The coefficient of the slope with 90% confidence intervals, on the log scale, will be calculated, using the pooled estimate of variance, and used to assess dose proportionality. Point estimates and confidence intervals for the slope will be reported to 2 decimal places

Pharmacokinetic Statistical Analyses for Dose Proportionality: ANOVA Method
Endpoint(s)

 AUC(0-6), Cmax Each endpoint to be assessed separately.
Model Specification

 The PK parameter will be dose-normalised prior to loge-transformation by multiplying by reference dose / dose Dose will be fitted as a fixed effect, subject as a random effect using DDFM=KR. The reference dose will be chosen based on the lowest clinically relevant dose over which PK can be adequately described, with each other dose as the test doses in the construction of the ratio $\mu(\text{test})/\mu(\text{reference})$.
Model Results Presentation

Pharmacokinetic Statistical Analyses for Dose Proportionality: ANOVA Method

 • Point estimates for the adjusted means on the log_e scale, the mean difference between each dose (test) and the reference dose and associated 90% confidence interval will be constructed using the residual variance. These will not be presented. • The point estimate and confidence interval will then be exponentially back-transformed to allow the presentation of the adjusted (least square) geometric means for each treatment (dose), and point estimates and associated 90% confidence intervals for the ratio test/reference. • Point estimates and 90% confidence intervals for AUC, Cmax will be reported to 2 decimal places. Ratios and 90% CIs will be plotted by dose. • Plots will also be provided showing the adjusted geometric mean ratio of test to reference treatment (dose) for AUC(0-6), and Cmax together with 90% confidence interval.

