4.2.1. Starting Dose and Dose Escalation

The first dose to be administered in this study will be a single dose of 500 mcg GSK3923868 inhalation powder in treatment period 1 followed by a single dose escalation to 1000 mcg GSK3923868 inhalation powder in treatment period 2.

The 1500 mcg GSK3923868 inhalation powder once daily dose given for 14-days in treatment period 3 will be the highest dose level to be evaluated in this study. This dose was half of the highest dose administered (3000 mcg) that was well tolerated in the FTIH Study [GSK Document Number [2020N430088_03](#)], including administration for 7 days to participants with asthma.

[figure not shown]

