6.1. Study Intervention(s) Administered

Table 3 Study Intervention(s) Administered

Study Intervention				
Treatment:	Single Dose Period 1	Single Dose Period 2	Repeat Dose (Period 3)	All Treatment Periods
Intervention name:	GSK3923868 [REDACTED] for inhalation.			Placebo to match GSK3923868 [REDACTED] for inhalation.
Type:	Drug			Placebo
Dose Formulation:	[REDACTED] containing inhalation powder blend. Delivered via [REDACTED] device.			
Unit Dose Strength:	500 mcg	1000 mcg	500 mcg	N/A
Dosage Level(s)¹:	[REDACTED] [REDACTED]	[REDACTED] [REDACTED]	[REDACTED] [REDACTED]	Number [REDACTED] to match active treatment.
Route of Administration:	Inhalation			
Use:	Experimental			Placebo
IMP and NIMP:	IMP			
Sourcing:	Provided centrally by the Sponsor			
Packaging and Labelling:	Study Intervention will be provided in a [REDACTED]. [REDACTED] and one 8 g 20% RH maintaining desiccant sachet. Each [REDACTED] will be labelled as required per country requirement.			
Current Name:	N/A	N/A	NA	N/A

¹[REDACTED].

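### The dose-proportionality rule cancels the whole analysis over non-calculable values at 1000 mcg, a dose that carries about 1.5% of the slope information

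*SAP*

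**What the plan says.** Protocol 9.4.3 commits to an analysis of dose proportionality and leaves the method to the SAP. SAP 4.3.1.3 makes the power model primary and an ANOVA on dose-normalised values supportive, for AUC(0-6) and Cmax. On the data used it says: "The assessment of dose proportionality will utilise Period 1,2 and the first dose of Period 3 data only".

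Three conditions govern whether the analysis is run:

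- It is done only "if more than 5 subjects have well defined plasma profiles". The text does not say whether this count applies to each dose, though the next sentence, which speaks of a dose with limited data, implies that it does.
- "If the dose with limited data is at the lower end of the dose range, the data will be excluded", and the remaining doses are analysed.
- However, "if there are non-calculable PK parameter data at intermittent doses no statistical analyses will be performed".

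Protocol 4.2.1 gives the doses. Period 1 is a single dose of 500 mcg, Period 2 is "a single dose escalation to 1000 mcg GSK3923868 inhalation powder in treatment period 2", and 1500 mcg in Period 3 is the highest dose level. There is therefore one intermediate dose, 1000 mcg. The SAP gives no reason for treating the two shortfalls differently, no rule for a short highest dose and no minimum dose range.

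**The concern.** The power model regresses log exposure on log dose, so its precision depends on how far apart the doses lie. The middle of three doses sits close to the mean log dose and has little influence on the slope. The rule nevertheless stops everything when the middle dose has a gap. When the lowest dose is short, it carries on with two doses that differ only 1.5-fold.

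Two things are at stake. An analysis that the protocol says will be conducted could be dropped while the data still support it almost fully. That includes the 1500/500 ratio from the ANOVA, which needs no 1000 mcg data. Conversely, a slope too imprecise to separate proportional from clearly non-proportional exposure could be presented as the primary assessment.

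**Working it through.** **Inputs from the documents.** Doses 500, 1000 and 1500 mcg (Protocol 4.2.1). Up to 9 on active per dose, with a smaller scenario of 6 (SAP 5). Four sequences of 3 participants: A-P-A, A-A-P, A-A-A and P-A-A (SAP 1.2). Power model with no subject term written and a 90% CI for the slope (SAP 4.3.1.3). Kenward-Roger degrees of freedom and a repeated-measures covariance structure are named for these analyses in SAP 4.3.1.5.

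**The plan's own figures.** The SAP states no precision for the slope, so there is nothing to reproduce on this point. The group sizes can be checked against its adverse-event probabilities. For n = 9, 1 − 0.95^9 = 0.370 and 1 − 0.80^9 = 0.866 (stated 37% and 87%). For n = 6, 0.265 and 0.738 (stated 27% and 74%). All agree.

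**Slope information by dose.** ln(dose) = 6.215, 6.908, 7.313, with mean 6.812. Squared distances from the mean are 0.357, 0.009 and 0.251, summing to 0.617. The shares are 57.8% (500 mcg), 1.5% (1000 mcg) and 40.7% (1500 mcg).

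**Power model as written.** SE(slope) = σ/√Sxx, where Sxx is the sum of squares of ln(dose) about the mean of the doses retained, with 9 values per dose.

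| Doses kept | Sxx | SE | Ratio to all doses | df | 90% CI width ratio |
|---|---|---|---|---|---|
| All three | 5.555 | 0.424σ | 1.00 | 25 | 1.00 |
| 500 + 1500 (analysis cancelled) | 5.431 | 0.429σ | 1.01 | 16 | 1.03 |
| 1000 + 1500 (analysis reported) | 0.740 | 1.163σ | 2.74 | 16 | 2.80 |

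If 5 of 9 profiles remain at 1000 mcg, the SE rises by 0.4%. With 6 per dose the SE ratios are unchanged, and the CI width ratios become 1.05 and 2.85.

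**With a random subject intercept.** Generalised least squares on the four sequences, assuming between-subject SD 0.4 to 0.5 and within-subject SD 0.2 to 0.4 on the log scale (the documents give neither). Without 1000 mcg the SE ratio is 1.05 to 1.10; without 500 mcg it is 2.83 to 2.99. At the extreme where only within-subject contrasts count, the SE ratios are 1.13 and 3.06. Degrees of freedom then fall from 14 to 5, so the CI width ratios are 1.29 and 3.50.

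**On the slope scale.** Half-width of the 90% CI = t × SE. For an assumed residual CV of 30%, σ = √ln(1.09) = 0.294:

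- all doses: 1.708 × 0.424 × 0.294 = 0.21
- 500 + 1500: 1.746 × 0.429 × 0.294 = 0.22
- 1000 + 1500: 1.746 × 1.163 × 0.294 = 0.60

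Over an assumed CV of 20 to 50% the ranges are 0.14 to 0.34, 0.15 to 0.35 and 0.40 to 0.96.

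**The case against.** **Excluding a short lowest dose has a sound rationale.** If profiles are short because concentrations are non-quantifiable, the values that remain at 500 mcg are selected upwards and would bias the slope. SAP 3 anticipates non-quantifiable values. A reader might infer that the rule is simply the wrong way round and that the low-dose exclusion should go. The documents do not support that: precision is only one criterion, and the exclusion can be right on grounds of bias. The rationale does not, however, make a 1.5-fold slope informative, and it does not explain cancelling the analysis when 500 and 1500 mcg are both adequate.

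**The trigger may be rare.** Withdrawn participants leave the study and replacements restart at Period 1 (Protocol 4.1, 7.1 and 7.2), so dropout before Period 2 costs 1500 mcg as well as 1000 mcg. Low exposure should affect 500 mcg first. If the threshold of more than 5 also governs the cancelling sentence, four of nine profiles would have to be lost at 1000 mcg alone. This stands as a limit on likelihood. It weakens at 6 per dose, where one lost profile is enough, and it does not apply to the literal reading, which has no count.

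**Two doses cannot show curvature.** This is true of 500 + 1500, but equally of 1000 + 1500, so it does not justify the asymmetry.

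**The loss is more than 1% in a paired analysis.** This is also true. Lost degrees of freedom can widen the CI by up to 29% at the within-subject limit, still far below the 3.5-fold widening without 500 mcg.

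**The consequences are limited.** No hypothesis is tested, the section sets no acceptance limits, the CI shows the imprecision, and PK data are summarised descriptively in any case (SAP 4.3.1.2).

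**Conclusion.** The cancelling sentence should not stand. It removes a planned analysis when the loss is about 1% in SE under the model as written, or about 5 to 10% with a random subject intercept. The plan proceeds when the loss is 2.7- to 3.0-fold. The ratios for the model as written depend only on the doses and on equal numbers per dose; the others rest on the assumed variances, and the half-widths on an assumed CV. The ordering held in every model tried. Two readings are also needed: that the intermittent doses are intermediate ones, and that the planned doses are not modified.

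A reader of Protocol 6.1, Table 3, might also infer that the retained 1000 versus 1500 mcg comparison is confounded with unit strength, because the "Unit Dose Strength" row differs between Periods 2 and 3. The documents do not establish this as a bias. The dosage-level cells are redacted and no delivered dose by strength is given, so any size would be invented.

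This is a worthwhile correction to a secondary PK analysis. It does not affect the primary safety objective.

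**What to change.** In SAP 4.3.1.3:

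1. Delete the sentence that cancels the analysis for intermediate doses. Replace it with a rule that the power model, and the ratio of highest to lowest dose from the ANOVA, are fitted to all calculable values when the lowest and highest doses each have more than 5 evaluable profiles, whatever the number at 1000 mcg. Say that the threshold applies per dose.
2. State that if only two doses contribute, linearity on the log scale cannot be checked.
3. The exclusion of a short lowest dose may stay. Add that a slope from 1000 and 1500 mcg alone is descriptive, is shown with its 90% CI and is not used to conclude proportionality.
4. While the text is open, say what happens if the highest dose is short, since the SAP is silent on this.

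The core change (items 1 and 3) is about two sentences of SAP wording and needs no new data or design change. What is given up is presenting a 1000/1500-only slope as the primary assessment.
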